### **8.3. Patient Withdrawal Criteria**

Patients may be discontinued from the study for the following reasons:

- Death
  - An autopsy will be requested for any patient who expires following participation in a gene replacement study as per the National Institutes of Health’s Guidelines for Research Involving Recombinant or Synthetic Nucleic Acid Molecules [25] (see Autopsy Plan in [Appendix 2](#))
- Failure to comply with protocol-required visits or study procedures for 3 or more consecutive visits that are not rescheduled, unless due to hospitalization
- Parent(s)/legal guardian(s) withdraws consent
- Investigator discretion

Early termination procedures should be completed within 14 days for any patient who prematurely discontinues the study for any reason, as indicated in [Appendix 1](#).

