All post-treatment visits will be relative to the date on which gene replacement therapy is administered, except for the 14 and 18 months of age visits, which will be relative to the patient's date of birth. For the 14 and 18 months of age visits, the patient will return within 0 to 14 days **after** the date on which the patient reaches 14 and 18 months of age, respectively. The 18 months of age visit will also serve as the End of Study visit. After the End of Study visit, eligible patients will be asked to roll over into the long-term follow-up study.

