## **10.7. Dose Adjustment Criteria**

The study investigates a one-time IV infusion of AVXS-101; no dose adjustments are possible.

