### **11.3. Video Evidence**

Physical therapy assessments (Bayley Scales and CHOP-INTEND) required at each study visit will be video recorded in an effort to produce compelling, demonstrable, documented evidence of efficacy, as determined by changes in functional abilities. AveXis, Inc. (AveXis) will provide a secure and confidential upload process for transfer and storage of the videos from investigational sites to a contracted third-party vendor that will compile and arrange videos as per AveXis requirements. Any/all videos received at AveXis or the contracted vendor will be treated as confidential study data and will be the sole property of AveXis. AveXis and the contracted vendor will provide this secure, encrypted transfer and storage solution to properly protect the identities of patients/families on the videos, which may be shared with regulatory agencies, the medical community, and/or in appropriate venues to discuss the results of this clinical study.

Videos may be provided to an independent, centralized reviewer for unbiased assessment of developmental milestone achievement. The independent reviewer will document whether the video displays evidence of having achieved each developmental milestone. The date of developmental milestone achievement will be computed as the earliest date on which video evidence demonstrates the achievement of the specified milestone.

Additionally, the Parent(s)/legal guardian(s) may submit additional videos demonstrating achievement of developmental milestones at any time during the study. These videos will be handled in the same manner in which the study-derived videos are handled.

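### Section 8.3 lets infused children leave follow-up without later ascertainment of the fixed-age outcomes, which can bias the 14-month survival co-primary

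*Protocol*

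**What the plan says.** Section 8.3 opens with "Patients may be discontinued from the study for the following reasons". The list includes "Failure to comply with protocol-required visits or study procedures for 3 or more consecutive visits that are not rescheduled, unless due to hospitalization" and, with no criterion attached, "Investigator discretion". What follows is fixed in the same section: "Early termination procedures should be completed within 14 days for any patient who prematurely discontinues the study for any reason".

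Treatment is over by then. Section 10.7 says: "The study investigates a one-time IV infusion of AVXS-101; no dose adjustments are possible".

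Both co-primary endpoints are tied to age. Section 7.1 schedules the visits so that "the patient will return within 0 to 14 days after the date on which the patient reaches 14 and 18 months of age, respectively". Survival, meaning freedom from death and permanent ventilation, is judged at 14 months of age, and sitting at the 18-month visit.

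Other routes by which a discontinued child's outcome might reach the database are limited:

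- Long-term follow-up (7.1): "After the End of Study visit, eligible patients will be asked to roll over into the long-term follow-up study". It comes after the visit that a discontinued child does not reach.
- Ventilator hours (12.1.7) are read from a card in the machine that the family brings to visits.
- Family video (11.3): "the Parent(s)/legal guardian(s) may submit additional videos demonstrating achievement of developmental milestones at any time during the study". This does not clearly cover the time after discontinuation.
- Adverse events and SAEs (13.3, 13.4) are recorded to the last study visit. After that, only SAEs considered related that the investigator comes across are to be reported.

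For the analysis, section 14.3.1 uses observed data when data are missing. Section 14.2 allows for about 30% of the 15 ITT patients being left out.

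**The concern.** Rules of this kind suit a drug that can be stopped. Here the exposure cannot be withdrawn, so discontinuing a child ends only the observation of a fixed-age outcome. No analysis convention can recover a 14-month ventilation status that was never sought, so this is a matter of data collection and not something to leave to the SAP.

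With about 15 children, a few unknown outcomes carry weight. The study is open-label, and whoever exercises the discretion knows how the child is doing. A family may also find visits harder as the disease advances. If children heading towards an event leave first and are then dropped, the observed survival proportion overstates the true one.

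**Working it through.** **Inputs.** All are from section 14.2 except the observed-data rule (14.3.1). There are 15 ITT patients with about 30% excluded: 15 × 0.70 = 10.5, so 10 or 11 are analysed. Survival is 80% on treatment against 25% in 26 controls, with a two-sided Fisher's exact test at 0.05. Sitting is tested against 0.1%, with true rates of 30% to 40%, by a one-sided exact test at 0.025. Because 25% of 26 is 6.5, results are shown for both 6/26 and 7/26.

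**The plan's own power figures.** Survival power is the sum of Bin(x; n, 0.80) × Bin(y; 26, 0.25) over all tables with Fisher p ≤ 0.05. It is 81.9% for n = 10 and 85.9% for n = 11, so the stated figure above 80% reproduces. For sitting, one responder is enough, so power is 1 − (1 − p)ⁿ. At p = 0.30 this is 1 − 0.7¹⁰ = 97.2% and 1 − 0.7¹¹ = 98.0%, so the stated figure above 90% also reproduces. The issue is therefore bias, not power. With all 15 children followed, survival power would be 92.6%.

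**Effect of selective loss on survival.** Each p-value sums the hypergeometric probabilities C(n,x)·C(26,y)/C(n+26,x+y), with margins fixed, over tables no more probable than the one observed. Assume that 8 of 15 truly survive event-free (53%) and that k of the 7 children with events are discontinued before the event and dropped. Both are assumptions, not protocol figures.

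| Children dropped (k) | Observed | p vs 6/26 | p vs 7/26 |
|---|---|---|---|
| 0 | 8/15 | 0.086 | 0.108 |
| 1 | 8/14 | 0.043 | 0.089 |
| 2 | 8/13 | 0.033 | 0.079 |
| 3 | 8/12 | 0.014 | 0.033 |
| 4 | 8/11 | 0.008 | 0.025 |

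Four losses are 4/15 = 27%, within the planned allowance. The observed survival proportion rises from 53% to 8/11 = 73%, and the test changes from not significant to significant. One loss is enough against 6/26, and three against 7/26.

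**The opposite direction.** If the four lost children are all survivors, 4/11 gives p = 0.44 or 0.70.

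**Sitting.** One sitter among 15 gives an exact p of 1 − 0.999¹⁵ = 0.015, below 0.025. With 10 or 11 analysed it is 0.010 or 0.011. A few losses seldom change that test.

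**The case against.** Several points on the other side are sound.

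- **The wording is permissive.** Section 8.3 says that patients may be discontinued, and section 7.1 asks for missed visits to be rescheduled within 7 days. No child has to be removed. A reader might infer that the rules force withdrawal; the text does not say so.
- **Some of the sickest children are protected.** Absence due to hospitalization is exempt, and families unable to travel for repeat visits are excluded at entry (8.2, criterion 16). No frequency is given for either ground, so it is not shown that those lost would be the ones doing worst. The exemption still does not cover a child who later becomes too frail to travel, and the discretion ground has no criterion.
- **Some provision exists.** Qualifying infused children stay in the ITT population (14.1.2.1), and patients who meet discontinuation criteria are in the efficacy completers population (14.1.2.2). The early-termination visit includes a Bayley assessment and a pulmonary examination. None of this supplies a later 14- or 18-month outcome.
- **The version matters.** The full text available is version 2.0, and version 1.0 has the same withdrawal wording. The end of a later summary of changes is also present, but not a later section 8.3.

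A reader might also infer that three withdrawals could overturn the planned result. With 12/15 survivors against 7/26, p = 0.0014. Counting three of those survivors as failures gives 9/15 and p = 0.051 (0.041 against 6/26). The protocol states no such imputation. Under its observed-data rule the same losses give 9/12, with p = 0.012 or 0.004, still significant.

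**Conclusion.** The gap is real and worth closing. In the text available, an infused child can leave observation on two non-consent grounds, and nothing requires the 14-month survival and ventilation status or the 18-month outcomes to be sought afterwards. Together with the observed-data rule, this can bias the survival co-primary. In the illustration, up to four selective losses move p from 0.086 to 0.008 (6/26) or from 0.108 to 0.025 (7/26). That rests on an assumed true survival of 8/15, loss before the event, and dropping the lost children. It shows what the rule could do, not what is expected.

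A child discontinued after 14 months of age loses only the 18-month outcomes. The documents do not support reading this as a serious threat to the sitting test, or as a flaw in the stated power. The point should be checked against the current section 8.3 before action.

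**What to change.** Add a paragraph to section 8.3. After infusion, missed visits and investigator discretion end only scheduled procedures. Unless the parents withdraw consent to contact or to records, the site then:

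- ascertains vital status, tracheostomy and ventilation use at 14 months of age, from device data or the medical record where available;
- seeks the 18-month sitting assessment by visit or, failing that, by family video under section 11.3, flagged as not obtained at the study visit;
- records SAEs to 18 months of age.

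The cost is an amendment paragraph, a consent line, and a few telephone or record contacts for the children affected. There is also a price in quality. The endpoint definitions expect device-based ventilator hours and a video-confirmed item at the study visit, so ventilation and sitting data for these children will be less standardised. Telephone contact alone is reliable mainly for vital status and tracheostomy. No treatment changes.

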## 9. TREATMENT OF PATIENTS

It is the responsibility of the Investigator to ensure the safe storage and administration of gene replacement therapy.

### 9.1. Description of Product

The biological product is a non-replicating recombinant AAV9 containing the complimentary deoxyribonucleic acid (cDNA) of the human SMN gene under the control of the cytomegalovirus (CMV) enhancer/chicken- $\beta$ -actin-hybrid promoter (CB). The AAV inverted terminal repeat (ITR) has been modified to promote intramolecular annealing of the transgene, thus forming a double-stranded transgene ready for transcription. This modified ITR, termed a “self-complementary” (sc) ITR, has been shown to significantly increase the speed of which the transgene is transcribed and the resulting protein is produced. The biological product, called AVXS-101 (formerly scAAV9.CB.hSMN), expresses the human SMN protein in transduced cells.

**Table 5: Investigational Product**

	Investigational Product
Product Name:	AVXS-101
Dosage Form:	Equivalent to the dose received by the second dosing cohort in the Phase 1 study
Unit Dose	1.1 X 10  vg/kg; Equivalent to the dose received by the Cohort 2 in the Phase 1 study (AVXS-101-CL-101) as determined by direct product testing with improved analytical methods.
Route of Administration	Intravenous infusion
Physical Description	AVXS-101 is a clear, colorless liquid.

### 9.2. Prior and Concomitant Medications

Prior and concomitant medications will be captured in the electronic Case Report Form (eCRF) from 2 weeks prior to administration of gene replacement therapy through the last study visit.

#### 9.2.1. Prophylactic Administration of Prednisolone

An antigen specific T-cell response to the AAV vector was observed in the ongoing Phase 1 clinical study (AVXS-101-CL-101) investigating AVXS-101 treatment via IV infusion. This is an expected response between 2 to 4 weeks following gene replacement therapy. One possible consequence to such antigen specific T-cell response is clearance of the transduced cells and loss of transgene expression.

In an attempt to dampen the host immune response to the AAV-based therapy, all patients will receive prophylactic prednisolone at approximately 1 mg/kg/day beginning 24 hours prior to gene replacement therapy until at least 30 days post-infusion. After 30 days of treatment, the dose of prednisolone can be tapered for patients whose ALT values, AST values, and T-cell response are below the threshold of  $\leq 2 \times \text{ULN}$  for ALT and AST, and  $< 100 \text{ SFC}/10^6 \text{ PBMCs}$  in accordance with the following treatment guideline:

- Until at least 30 days post-infusion: 1 mg/kg/day
- Weeks 5 and 6: 0.5 mg/kg/day
- Weeks 7 and 8: 0.25 mg/kg/day
- Week 9: prednisolone discontinued

If the AST or ALT values are  $> 2 \times$  ULN, or if T-cell response is  $\geq 100$  SFC/ $10^6$  PBMCs after 30 days of treatment, the dose of prednisolone will be maintained until the AST and ALT values decrease below threshold. If T-cell response continues past Day 60, Investigator discretion should be used considering risk benefit for maintaining prednisolone. Variance from these recommendations will be at the discretion of the Investigator based on potential safety issues for each patient.

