- n Serious adverse events are collected from signing of the informed consent through the last study visit. All adverse events that occur from the start of gene replacement therapy through the last study visit are collected.
- o Laboratory samples collected on Day -1 to be processed locally, prior to dosing.
- p Sites participating in the viral shedding sub-study will collect 24-hour full volume samples for urine and feces at 24 and 48 hours. All other sites will collect singular urine and feces samples within 24 hours and 48 hours of dosing.
- q Prednisolone to be given 24 hours prior to scheduled AVXS-101 dosing, and continued as per protocol [Section 9.2.1](#).
- r CK-MB to be performed at Day 60, ~~and every 90 days (Month 6, 9, 12-months of age,~~ 15 months of age, 18 months of age/EOT).
- s **If a Day -1 CHOP-INTEND assessment is not completed, a CHOP-INTEND assessment should be completed on Day 1 prior to dose administration.**

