In an attempt to dampen the host immune response to the adeno-associated virus (AAV) derived therapy, all patients will receive prophylactic prednisolone at approximately 1 mg/kg/day beginning 24 hours prior to AVXS-101 infusion until at least 30 days post-infusion. After 30 days of treatment, the dose of prednisolone can be tapered for patients whose alanine aminotransferase (ALT) values, aspartate aminotransferase (AST) values, and T-cell response are below the threshold of 2 X ULN for ALT and AST, and < 100 SFC/10^6 PBMCs in accordance with the following treatment guideline: 1 mg/kg/day until at least 30 days post-infusion, 0.5 mg/kg/day at Weeks 5 and 6, 0.25 mg/kg/day at Weeks 7 and 8, and discontinued at Week 9.

Efficacy will be assessed by achievement of the key developmental milestone of functional independent sitting for at least 30 seconds at the 18 months of age study visit and survival at 14 months of age. The ability to thrive (as defined above) and the ability to remain independent of ventilatory support (as defined above) will also be assessed at 18 months of age. Additional developmental milestones will be assessed using Bayley Scales of Infant and Toddler Development (Version 3). Safety will be assessed through monitoring adverse events (AEs), concomitant medication usage, physical examinations, vital sign assessments, cardiac assessments, and laboratory evaluations. A Data Safety Monitoring Board (DSMB) will review safety data on a quarterly basis, and will also convene within 48 hours should any patient experience an unanticipated CTCAE Grade 3, or higher AE/toxicity that is possibly, probably, or definitely related to gene replacement therapy, and is associated with clinical symptoms and/or requires

medical treatment. This includes any patient death, important clinical laboratory finding, or any complication attributed to administration of gene replacement therapy. In such instances, the DSMB will review the safety information and provide its recommendation. The DSMB can recommend early termination of the study for safety reasons.

**Number of Patients (planned):** Up to twenty (20) patients that meet the study enrollment criteria to enable at least fifteen (15) patients that meet ITT criteria. Study enrollment will stop as soon as practical following enrollment of the fifteenth patient that meets the ITT criteria.

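### Section 9.2.1 (Protocol version 2.0): a T-cell response alone starts the prednisolone hold, but the stated end of the hold names only AST and ALT

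*Protocol*

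**What the plan says.** Section 9.2.1 of Protocol version 2.0 sets the steroid rule after the first 30 days in four linked statements.

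- **Taper rule.** The dose may be "tapered for patients whose ALT values, AST values, and T-cell response are below the threshold". The limits are 2 × ULN for the enzymes and 100 SFC/10⁶ PBMCs for the T-cell response. The Methodology part of the synopsis names the same three markers: "aspartate aminotransferase (AST) values, and T-cell response are below the threshold of 2 X ULN for ALT and AST", followed by the T-cell limit.
- **Hold.** The hold starts if AST or ALT is above 2 × ULN, "or if T-cell response is" at or above 100 SFC/10⁶ PBMCs. In that event "the dose of prednisolone will be maintained until the AST and ALT values decrease below threshold".
- **Day 60.** "If T-cell response continues past Day 60, Investigator discretion should be used considering risk benefit for maintaining prednisolone".
- **Variance.** "Variance from these recommendations will be at the discretion of the Investigator based on potential safety issues for each patient".

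The hold sentence is identical in Section 9.2.1 of version 1.0, and the summary of changes for version 2.0 (Appendix 8) lists no change to that section.

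**The concern.** The hold can start on any of three markers, but its stated end mentions two. The missing one is the marker the steroid is there to control. Section 9.2.1 says that prednisolone is given to dampen the immune response to the vector. It describes a T-cell response as expected 2 to 4 weeks after dosing, and it names clearance of transduced cells and loss of transgene expression as a possible consequence. The product is given once, with no dose adjustment (Section 10.7).

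The situation can arise in ordinary conduct. ELISpot is scheduled at Day 30, which is when the taper decision is made. A site that took the written end of the hold as leave to taper would reduce the steroid while the T-cell response persisted.

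**Working it through.** **Logic of the three rules.** Each of AST, ALT and T-cell response is either high or below threshold, which gives 2 × 2 × 2 = 8 combinations after Day 30.

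| Enzymes | T-cell response | Combinations | Hold triggered? | Written end of hold | Taper rule |
|---|---|---|---|---|---|
| Both below | Below | 1 | No | Not applicable | Taper allowed |
| At least one high | Below | 3 | Yes | When enzymes fall | Agrees with the end |
| At least one high | High | 3 | Yes | When enzymes fall, even if T-cell response is still high | Still bars taper |
| Both below | High | 1 | Yes | Already met at the start | Bars taper |

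The hold is triggered in 7 of the 8 combinations. In 3 of those 7 its end agrees with the taper rule. In 1 the end is met before the hold begins, so the hold either does nothing or has no defined end. In the other 3 the hold can end while the taper rule still forbids a reduction.

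The Day 60 sentence does not fill the gap. It applies only after Day 60, and it presupposes that a persisting T-cell response has kept the child on prednisolone until then, which the end condition does not say. The variance sentence permits departures for safety; it does not state what the rule is for Days 30 to 60.

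**Worst-case dose difference, Days 31–60.** Inputs from Section 9.2.1: 1 mg/kg/day to Day 30, 0.5 in Weeks 5–6, 0.25 in Weeks 7–8, none from Week 9. Assumption: the T-cell response stays high throughout and the site tapers anyway.

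- Dose held: 30 × 1 = 30 mg/kg.
- Taper on calendar weeks (Weeks 5–6 are Days 29–42, Weeks 7–8 are Days 43–56): 12 × 0.5 + 14 × 0.25 + 4 × 0 = 9.5 mg/kg. Difference 30 − 9.5 = 20.5 mg/kg; ratio 30/9.5 ≈ 3.2.
- Taper with both 14-day steps counted from Day 31: 14 × 0.5 + 14 × 0.25 + 2 × 0 = 10.5 mg/kg. Difference 30 − 10.5 = 19.5 mg/kg; ratio 30/10.5 ≈ 2.9.
- Site follows the taper rule: difference 0.

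**After the fix.** If the hold ends only when all three markers are below threshold, the end is the exact complement of the trigger and agrees with the taper rule in all 8 combinations.

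**The case against.** The strongest reply is that Section 9.2.1, read as a whole, already gives the right dose. The end of an instruction to maintain is not in itself permission to reduce. Permission comes only from the taper rule, which requires the T-cell response to be below threshold, and the synopsis repeats that. Persisting T-cell response has its own sentence, and the Investigator may depart from the scheme for safety. This largely stands. It settles what was intended and keeps the consequence small. It does not make the clause correct, because a site still has to set aside an explicit end condition to reach the intended dose.

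A reader might infer that the protocol directs sites to taper a child whose T-cell response persists, or that treated children would be under-dosed by about 20 mg/kg. The documents support neither. The taper rule forbids that reduction, the dose figure needs a misreading plus a response that lasts the whole 30 days, and the number of children in this position is not given.

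It is also fair to object that the repair is not free. ELISpot is scheduled only at Day 7 and Day 30 (Section 12.1.10.6), later sampling is optional, and the blood-volume maximum in Table 6 assumes no elevated Day 30 response. That stands, though the existing taper rule already implies a repeat test.

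**Conclusion.** The clause is wrong as written in version 2.0: between Day 30 and Day 60 the end of the hold contradicts both its own trigger and the taper rule. The intended rule can be recovered from the section, so the consequence is limited to a site that treats the written end as leave to taper. The dose lost would then be at most 19.5 to 20.5 mg/kg over Days 31–60, and zero otherwise. No efficacy test, error rate or sample size changes. It should be corrected because it is a dosing rule for infants and the correction is short.

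One limit applies. The file opens with the tail of a later amendment's change summary. Its schedule footnote q still points to Section 9.2.1 ("Prednisolone to be given 24 hours prior to scheduled AVXS-101 dosing, and continued as per protocol"), but the amended wording of that section is not shown. A reader might infer that the fault persists in the latest protocol, or that it was repaired; neither can be established here, and the later text should be checked.

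**What to change.** Replace the end condition in Section 9.2.1 and join the Day 60 sentence to it, along these lines: *prednisolone stays at the same dose until AST, ALT and T-cell response are all below threshold; if the T-cell response alone is still at or above threshold past Day 60, the Investigator decides whether to continue after weighing risk and benefit.* Stating the Day 60 limit in the same sentence keeps the hold from being read as open-ended. Leave the variance sentence unchanged.

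The cost is one sentence, plus a repeat ELISpot for children whose Day 30 result is elevated. Each needs 4–6 mL of whole blood, so one repeat would take the 96.2 mL maximum in Table 6 to between 96.2 + 4 = 100.2 and 96.2 + 6 = 102.2 mL. Note a to Table 6 and Section 12.1.10.6 already foresee such samples.
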